4.1 Design overview -amended

[figure not shown]
In this multinational, multicenter, randomized (1:1), double-blind, placebo-controlled, parallel-group study, a total of approximately 200 patients are planned for enrollment in order to randomize up to⁹ approximately 130 patients to study drug treatment (approximately 65 patients to the riociguat group and 65 to the placebo group).

The study design consists of a main treatment phase followed by a long-term extension phase as follows (see [Figure 4–1](#) and [Figure 4–2](#)):

- **Screening phase:** up to 2 weeks
- **Main treatment phase:** 52 weeks of double-blind treatment, consisting of:
 - Dose titration period of up to 10 weeks
 - Maintenance period of up to 42 weeks
- **Long-term extension phase**
 - Dose-titration period of up to 10 weeks (double-blind)
 - Open-label extension period
- **Termination visit and safety follow-up visit**

[figure not shown]
⁹ Per Amendment 5

Figure 4–1 Main treatment phase design

Abbreviations: V = visit; R = randomization; TID = 3 times a day.

Figure 4–2 Long-term extension phase design

Abbreviations: TID = 3 times a day; V = visit.

4.1.1 Screening phase (up to 2 weeks)

After providing written informed consent, patients will undergo a screening evaluation to determine their eligibility (see Section 7.1 for a detailed schedule of assessments). Patients will complete a diary including details on the number and duration of Raynaud's attacks per day for a period of 7 consecutive days leading up to Visit 1 / Day 0.

4.1.2 Main treatment phase (Week 0 to Week 52) - amended

At the baseline visit, patients who have met all of the inclusion and none of the exclusion criteria will be randomized via a telephone-based or web-based response system (IxRS) to receive treatment with either active study drug (riociguat) or placebo (Day 0, Visit 1).

Dose-titration period (Visits 1 to 6)

During the first 10 weeks of the main treatment phase, patients will undergo dose titration.

The starting dosage is 0.5mg TID. The dose should be increased by 0.5 mg increments no sooner than 2 weeks apart to 1 mg, 1.5 mg, 2 mg, and 2.5 mg TID, resulting in a maximum total daily dose of 7.5 mg. Patients will be maintained on a lower dose if higher doses are not tolerated (minimum dosage of 0.5 mg TID, total daily dose 1.5 mg; see Section 5.2.1).

To maintain blinding of the treatment arms, patients randomized to the placebo group will undergo sham titration from Visit 1 onwards during the dose-titration period according to the rules of the dose titration scheme. At Visit 6, the last visit of the Titration Phase, no further increase in study medication will be possible (see Figure 4-1)¹⁰.

Dose titration algorithm

The study medication dose for the next titration step will be determined every 2 weeks according to the patient's well-being and the peripheral systolic blood pressure (SBP) measured at trough before intake of the morning dose as well as based on any of the 2 measurements (supine or sitting) performed 2 hours after dose intake to assess orthostatic changes ¹¹according to the following algorithm (dose titration scheme):

- If SBP is ≥ 95 mmHg and the patient has no signs or symptoms of hypotension, the dosage should be increased by 0.5 mg TID.
- If SBP is < 95 mmHg, the dosage should be maintained provided the patient does not show any signs or symptoms of hypotension.
- If SBP is < 95 mmHg, and the patient exhibits signs or symptoms of hypotension, the current dosage should be decreased by 0.5 mg TID.

During the dose-titration period a dose reduction can be performed according to patient well-being / safety concerns at investigator's discretion irrespective of SBP. If the investigator requests an increase or decrease in study medication dose via IxRS, the subsequent dose modification will not exceed ± 0.5 mg TID. Dose increases are allowed after a down-titration provided it is not done sooner than two weeks apart.

¹⁰ Per Amendment 4

¹¹ Per Amendment 6

Maintenance period (Visits 7 to 12)

The overall duration of the main treatment phase is 52 weeks, including the dose titration period. At the end of the dose titration period (Week 10) the patient's maintenance dose will be determined using the treatment algorithm above. No further increase in dose will be allowed. The established dose will then be taken as the "optimal dose" to be administered for the remaining duration of the main treatment phase (up to Week 52).

Dose reductions for safety reasons (eg, in case of any treatment-emergent adverse event [TEAE]) are allowed, but a subsequent dose increase during the maintenance period is not permitted.

From Week 26 (Visit 10), patients will have the opportunity to add "rescue¹² therapy", consisting of immunosuppressant drugs, to their randomized study medication if they meet certain criteria for worsening skin or pulmonary disease. Please refer to Section 6.9 for further details.

4.1.3 Long-term extension phase

At Visit 12 (Week 52), patients randomized to the placebo arm in the main treatment phase will initiate active treatment with riociguat, as part of the long-term extension phase. During the first 10 weeks, a titration/sham-titration will be performed to maintain the study blind, after which the extension phase becomes open-label. During the extension phase, clinical outcomes will continue to be measured for exploratory long-term treatment effects. Adverse event information will continue to be collected during the extension phase as well.

The long-term extension phase will continue up to 6 years after the Last Patient Last Visit (LPLV) in the main treatment phase. Subsequent treatment should be discussed between the patient and his/her doctor during the final visit at the end of the extension phase. At the end of this study, it is expected that the patient will receive standard treatment at the discretion of the physician.

Dose-Titration period (Visits 12 to 17; Week 52 to 62)

At Visit 12 (Week 52), all patients will be assigned in IxRS to treatment with riociguat. To maintain the study blinding, neither the patient's prior treatment assignment nor dose will be unblinded. During the first 10 weeks of the long-term extension phase, patients previously on placebo will be up-titrated on riociguat according to the dose titration algorithm described above in the main treatment phase (Section 4.1.2). Patients randomized to riociguat in the main treatment phase will undergo sham titration to maintain the blinding during this period.

Open-label Extension period (Visit 18; Week 64 onward)

After completing the double-blind dose-titration period, from Week 64 onwards the study is open-label and the investigator will be able to see the current treatment dose. All patients will return to the clinic for visits every 3 months \pm 2 weeks. Ongoing titration of riociguat within the range of 0.5 mg to 2.5mg TID will remain at the discretion of the investigator, and dose reductions for safety reasons are allowed.

¹² Per Amendment 1

4.1.4 Dose Interruptions - amended

Although not intended, patients may interrupt their intake of study medication for various reasons (eg, hospitalization in a remote hospital without study medication access, safety reasons or side effects). If treatment is interrupted, the following rules should be applied:

Main treatment phase:

- ≤ 3 consecutive days without treatment (9 missing doses) in the dose-titration period: restart at the same dose
- > 3 consecutive days in the dose-titration period: discontinue¹³ the patient from study medication
- > 3 days but ≤ 14 consecutive days without treatment during the maintenance phase: treatment can be restarted at the discretion of the investigator at 0.5 mg TID lower than the last dose
- > 14 consecutive days without treatment in the maintenance phase: discontinue¹⁴ the patient from study medication.

Long-term extension phase:

- ≤ 3 consecutive days without treatment (9 missing doses) in the dose-titration period: restart at the same dose
- > 3 days but ≤ 14 consecutive days without treatment in the dose-titration period: treatment can be restarted at the discretion of the investigator at 0.5 mg TID lower than the last dose
- > 14 consecutive days without treatment in the dose-titration period: discontinue¹⁵ the patient from study medication.
- Interruptions in the **open-label extension period**¹⁶:
 - > 13 and ≤ 28 consecutive days: treatment can be restarted at the discretion of the investigator at 0.5 mg TID lower than the last dose.
 - > 28 consecutive days: discontinue the patient from study medication.

¹³ Per Amendment 4

¹⁴ Per Amendment 4

¹⁵ Per Amendment 4

¹⁶ Per Amendment 4 and Amendment 5

4.1.5 Termination visit and safety follow-up visit - amended

A termination visit should be performed for patients who discontinue¹⁷ from study medication for any reason except death or lost to follow-up, and should occur as soon as possible after the patient receives his/her last dose of study drug. In general, at the Termination Visit the same safety and efficacy relevant measurements and procedures should be performed as at Visit 12. If the discontinuation occurs before Visit 8 (Week 14), the skin biopsy and the blood samples for biomarkers are to be collected. No blood samples for pharmacokinetics (PK) have to be taken and vital signs post dose are not needed because no new medication will be dispensed to the patient. If the Termination Visit will be performed after Visit 12 (Week 52) the patient's and physician's global assessment, patient interference with skin assessment, and tender and swollen joint count assessment must not be performed.

A safety follow-up visit (30 [+5] days after the last dose of study medication) will be performed for all patients.

If the patient discontinues study drug¹⁸ prematurely during the main treatment phase (Week 0 – Week 52) he/she will be invited to come for limited assessments (mRSS, pulmonary function test [FVC and DL_{CO} (diffusion capacity of the lung for carbon monoxide) including hemoglobin measurement at the local laboratory]¹⁹, patient-reported outcomes [PROs], and patient's and physician's global assessment²⁰) at Week 12, Week 26, Week 39, and Week 52, depending on the timing of discontinuation²¹. The collection of these assessments is important for endpoint analysis which considers all assessments post baseline up to Week 52.

A detailed schedule of evaluations is presented in Section 7.1.1.

4.2 Primary variable

The primary efficacy outcome measure is the change in mRSS from baseline to Week 52.

4.3 Justification of the design

Riociguat has been safe and well tolerated in previous clinical studies at multiple doses between 0.5 and 2.5 mg TID in patients with PAH. Based on the positive results of riociguat in patients with PAH and CTEPH together with the compound's known antifibrotic effects as seen in *in vitro* and in animal models, patients with symptomatic dcSSc may benefit from treatment with riociguat. Currently, there is no approved therapy for dcSSc and no suitable active comparator in this target population. Therefore, the purpose of this study is to evaluate the efficacy and safety of riociguat versus placebo in patients with symptomatic dcSSc. The follow up time of 12 months has been chosen for the primary endpoint since it is considered an appropriate observation period to detect significant changes in the modified Rodnan Skin Score (mRSS) and is therefore used in many clinical studies with skin fibrosis.[15,16,17] Moreover, the 12-month trial duration is supported and validated by a 3-round Delphi consensus of measures for clinical trials of SSc [18]. See also Section 8.6 for further details.

¹⁷ Per Amendment 4

¹⁸ Per Amendment 1

¹⁹ Per Amendment 4

²⁰ Per Amendment 5

²¹ Per Amendment 4

4.4 End of study

For each participating EU country, the end of the study according to the EU Clinical Trial Directive will be reached when the last visit of the last patient for all centers in the respective country has occurred.

The end of the study as a whole will be reached as soon as the end of the study according to the above definition has been reached in all participating countries (EU and non-EU).

5. Study population

5.1 Eligibility

5.1.1 Inclusion criteria - amended

Patients must meet the following criteria to be eligible for enrollment in the study:

1. Written informed consent
2. Men or women aged 18 years and older
3. Systemic sclerosis, as defined by ACR/EULAR 2013 criteria[1]
4. dcSSc according to the LeRoy criteria[3] ie, skin fibrosis proximal to the elbows and knees in addition to acral fibrosis²².
5. Disease duration of ≤ 18 months (defined as time from the first non-Raynaud's phenomenon manifestation)
6. ≥ 10 and ≤ 22 mRSS units at the screening visit
7. FVC $\geq 45\%$ of predicted at screening
8. DL_{CO} $\geq 40\%$ of predicted (hemoglobin-corrected) at screening
9. Negative serum pregnancy test in a woman of childbearing potential at the screening visit
10. Women of childbearing potential must agree to use adequate contraception when sexually active. "Adequate contraception" is defined as any combination of at least 2 effective methods of birth control, of which at least 1 is a physical barrier (eg, condom with hormonal contraception like implants or combined oral contraceptives, condom with intrauterine devices). This applies since signing of the informed consent form until 30 (+5) days after the last study drug administration.
11. Ability to comply with the clinical visits schedule and the study-related procedures

5.1.2 Exclusion Criteria - amended

Patients who meet any of the following criteria will be excluded from enrollment in the study:

1. Medical and surgical history
 - Limited cutaneous SSc at screening
 - Major surgery (including joint surgery) within 8 weeks prior to screening

²² Per Amendment 4

- Patients with a history of malignancy in the last 5 years other than non-melanoma skin cell cancers cured by local resection or carcinoma in situ
 - Known hypersensitivity to the study drug (active substance or excipients)
2. Hepatic-related criteria
- Hepatic insufficiency classified as Child-Pugh C (see Appendix 14.1 for classification table)
 - Patients with isolated aspartate aminotransferase (AST) or ALT >3xULN (upper limit normal) or bilirubin >2xULN can be included in the trial under the condition of additional monitoring during the trial (see section 7.6.2)²³
3. Renal-related criteria
- Estimated glomerular filtration rate (eGFR) < 15 mL/min/1.73m² (Modification of Diet in Renal Disease [MDRD] formula) or on dialysis at the screening visit. Patients entering the trial with eGFR 15-29 mL/min/1.73m² will be undergo additional monitoring of renal function (see section 7.6.2)²⁴
 - Because the MDRD formula is thought to cause significant bias for Japanese patients, the equation for Japanese patients is:
194 x serum creatinine (mg/dL) -1.094 x Age -0.287 x 0.739 (if female).
 - Any prior history of renal crisis (see Appendix 14.2 for definition)
4. Cardiovascular-related criteria
- Sitting SBP <95 mmHg at the screening visit
 - Sitting heart rate <50 beats per minute (BPM) at the screening visit
 - Left ventricular ejection fraction <40% prior to screening
5. Pulmonary-related criteria
- Any form of pulmonary hypertension²⁵ as determined by right heart catheterization
 - Pulmonary disease with FVC <45% of predicted or DL_{CO} (hemoglobin-corrected) <40% of predicted at screening
 - Active state of hemoptysis or pulmonary hemorrhage, including those events managed by bronchial artery embolization
 - Any history of bronchial artery embolization or massive hemoptysis within 3 months before screening. (Massive hemoptysis is defined as acute bleeding >240 mL in a 24-hour period or recurrent bleeding >100 mL/day over consecutive days)
6. Laboratory examinations
- Patients with: hemoglobin <9.0 g/dL, white blood cell (WBC) count <3000/mm³ (<3 × 10⁹/L), platelet count <100,000/mm³ (<100 × 10⁹/L)²⁶

²³ Per Amendment 1

²⁴ Per Amendment 1

²⁵ Per Amendment 4 and Amendment 5

7. Prior and concomitant therapy

- Concomitant use of nitrates or NO donors (such as amyl nitrate) in any form, including topical; phosphodiesterase (PDE) 5 (PDE5) inhibitors (such as sildenafil, tadalafil, vardenafil); and nonspecific PDE5 inhibitors (theophylline, dipyridamole)
- Concomitant therapy with prostacyclin analogs. Oral beraprost for the treatment of digital ulcers / Raynaud's disease, and short-term / intermittent therapy of up to 21 days with intravenous prostacyclin analogs for digital / vascular lesions is allowed
- Treatment with methotrexate, cyclophosphamide, hydroxychloroquine, cyclosporine A, azathioprine, mycophenolate mofetil, rapamycin, colchicine, D-penicillamine, tacrolimus²⁷, mizoribine²⁸ or intravenous immunoglobulin within 4 weeks before the screening visit
- Treatment with etanercept within 2 weeks; infliximab, leflunomide, certolizumab, golimumab, adalimumab, abatacept or tocilizumab within 8 weeks; or anakinra within 1 week prior to the screening visit
- Previous treatment with chlorambucil, bone marrow transplantation, or total lymphoid irradiation
- Treatment with rituximab or other anti-CD20 antibodies within the last 6 months before screening

8. Other

- Pregnant women or breast feeding women
- Women of childbearing potential not willing to use adequate contraception (as defined in the aforementioned inclusion criteria, Section 5.1.1) and not willing to agree to 4-weekly pregnancy testing from Visit 1 (first administration of study drug) onwards until 30 (+5) days after last study drug intake.
- Any other condition or therapy that would make the patient unsuitable for this study and will not allow participation for the full planned study period
- Previous assignment to treatment during this study
- Participation in another clinical study with an investigational drug or medical device within 30 days prior to randomization (phases I–III clinical studies)

5.1.3 Justification of selection criteria

The selection criteria were carefully selected to exclude patients from the study who may potentially be exposed to specific risks after administering the study drug as well as patients with conditions that may have an impact on the aims of this study.

²⁶ Per Amendment 6

²⁷ Per Amendment 1

²⁸ Per Amendment 1

5.2 Withdrawal of patients from study - amended

5.2.1 Withdrawal²⁹ - amended

5.2.1.1 Withdrawal from the study³⁰

Patients *must* be withdrawn from the study for the following reasons:

- At their own request or at the request of their legally acceptable representative at any time during the study and without giving reasons, a patient may decline to participate further (withdrawal from study). The patient will not suffer any disadvantage as a result.
- Participation in another clinical trial after Visit 12. Participation in observational registries is allowed.

5.2.1.2 Discontinuation of study medication³¹

Patients *must* be discontinued from the study medication³² for the following reasons:

- If, in the investigator's opinion, continuation of the study would be harmful to the patient's well-being
- Occurrence of AEs or intercurrent diseases which the investigator judges unacceptable for continuation of participation in the study
- Occurrence of adverse drug reactions, which in the investigator's opinion have a negative impact on the patient's individual risk-benefit ratio. (Investigators are obliged to reassess the patient's individual risk-benefit ratio on a continuous basis. Factors such as anticipated treatment effect, progression of underlying disease, occurrence of side effects, and alternative treatment options must be considered.)
- If a subject, during the course of the study, develops
 - a) renal disease that leads to eGFR <15/mL/min/1.73m²,
 - b) hepatic insufficiency classified as Child-Pugh C³³.
- Non-compliance with the conditions for the trial or instructions by the investigator
- If treatment is interrupted for >3 consecutive days (9 doses)³⁴ during the dose titration period of the main treatment phase
- If treatment is interrupted for >14 consecutive days during the maintenance period of the main treatment phase or the dose-titration period of the long-term extension phase
- If treatment is interrupted for >28 consecutive days during the open-label extension period (of the long-term extension phase)³⁵
- In case of pregnancy or breast feeding.

²⁹ Per Amendment 4

³⁰ Per Amendment 4

³¹ Per Amendment 4

³² Per Amendment 4

³³ Per Amendment 5

³⁴ Per Amendment 1

³⁵ Per Amendment 4 and Amendment 5

- In case a female patient of childbearing potential is not compliant with 4-weekly pregnancy testing or with contraceptive measures.
- In case no further dose reduction is possible and the patient does not tolerate the lowest possible dosage (0.5 mg TID) of study drug

Patients *may* be discontinued from the study medication³⁶ for the following reasons:

- At the specific request of the sponsor and in liaison with the investigator (eg, safety concerns)
- A relative decline in FVC % predicted by $\geq 10\%$ (eg, a change of FVC from 60% to 54%) or a relative decline in FVC % predicted between 5 to $< 10\%$ with associated relative decline in DL_{CO} % predicted by $\geq 15\%$, provided that the decline in FVC results in FVC $< 75\%$ of predicted (confirmed by repeat pulmonary function testing within 1 month). Please refer to Section 6.9 for the option of adding rescue³⁷ therapy.
- An absolute increase in mRSS by > 5 units and $\geq 25\%$ (Please refer to Section 6.9 for the option of adding rescue³⁸ therapy), life-threatening or organ-threatening event attributable to SSc (such as renal crisis, digital gangrene, development of new PAH on right heart catheterization) or not attributable to SSc.

5.2.1.3 Handling of withdrawals or discontinuations from study medication³⁹

A patient who, for any reason (eg, failure to satisfy the selection criteria), terminates the study before the time point used for the definition of “dropout” (see below) is regarded a “screening failure”. Restarting the defined set of screening procedures to enable the “screening failure” patient’s participation at a later time point is not allowed.

One re-assessment of laboratory parameters is allowed during the screening phase to re-assess the eligibility of patients.

A patient who discontinues study participation prematurely for any reason is defined as a “dropout” if the patient has already been randomized.

Any randomized patient removed from the trial should undergo the assessments at the termination visit. The patient will remain under medical supervision until discharge or transfer is medically acceptable and will complete the 30-day safety follow-up period.

If the patient discontinues study drug⁴⁰ prematurely during the main treatment phase (Week 0 – Week 52) he/she will be invited to come for limited assessments (mRSS, pulmonary function test [FVC and DL_{CO} including hemoglobin measurement at the local laboratory]⁴¹, PROs, and patient’s and physician’s global assessment)⁴² at Week 12, Week 26, Week 39, and Week 52, depending on the timing of discontinuation⁴³. This will be in addition to the termination visit assessments (see Section 7.1.2.8), provided that the patient does not object to

³⁶ Per Amendment 4

³⁷ Per Amendment 1

³⁸ Per Amendment 1

³⁹ Per Amendment 4

⁴⁰ Per Amendment 1

⁴¹ Per Amendment 4

⁴² Per Amendment 5

⁴³ Per Amendment 4

collection of study data after withdrawal of consent. If the discontinuation occurs before Visit 8 (Week 14), the skin biopsy and blood samples for biomarkers are to be collected.

All reasons for discontinuation⁴⁴ (including lost to follow up), will be recorded in the electronic case report form (eCRF) and site medical record. Study medication assigned to the discontinued⁴⁵ patient may not be assigned to another patient.

In the event that a patient is lost to follow-up, every possible effort must be made by study site personnel to contact the patient to obtain complete data and determine the reason for discontinuation⁴⁶.

A patient may withdraw from further participation in the study and, unless he/she objects to further data collection, the following information should be obtained and documented in the eCRF⁴⁷:

- Vital status (at Week 52)
- Outcome of serious adverse events (SAEs)
- Efficacy endpoints at Weeks 12, 26, 39, and 52 (depending on timing of discontinuation of study medication)

The information should be collected in the eCRF until the safety follow-up visit 30 (+5) days after the last intake of study drug. Serious adverse events that occur within 30 (+5) days after the last dose of study drug will be followed up until resolution, if possible.

If patients refuse to be contacted via telephone (eg, patient objects to further release of information or are lost to follow-up), every effort should be made to obtain vital status (dead or alive) information at Week 52 through consultation of public databases, wherever allowed by local regulations⁴⁸.

The measures taken for follow up must be documented in the site medical record. Follow-up data will be collected for all randomized patients except those who specifically withdraw consent for release of such information, except as noted above. Thus, it is imperative to obtain complete data for all randomized patients, including information on efficacy and safety endpoint events, whether or not they receive study drug, or discontinue study drug prematurely.

Details for the premature termination of the study as a whole (or components thereof [eg, centers, treatment arms, dose steps]) are provided in Section 10.

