8.4.2.1 Primary endpoint¹²¹

The primary analysis will be the change in mRSS from baseline to all assessments post baseline up to Week 52 using mixed model repeated measures (MMRM) with baseline mRSS as a covariate, fixed effects treatment arm and region, the interaction effect between study visit and treatment arm, and patient specific random effects to account for both heterogeneity among patients and correlation among measurements taken on the same patient with an unstructured covariance assumption. The main estimand of interest is the treatment difference

¹²⁰ Per Amendment 1

¹²¹ Per Amendment 4

between the riociguat and placebo treatment arms at Week 52. The null hypothesis to be tested is no difference between riociguat and placebo at this visit.

The model statement is:

$$Y_{ij} = \mu + \beta X_i + t_k + r_l + v_j + (tv)_{jk} + s_i + \varepsilon_{ij}$$

where Y_{ij} is the change from baseline in mRSS to visit j for subject i that is in treatment group k and region l ; μ is the intercept, β is the baseline covariate effect, X_i is the baseline mRSS for subject i , t_k is the fixed effect of treatment k , r_l is the fixed effect of region l , v_j is the fixed effect of visit j , $(tv)_{jk}$ is the interaction effect of treatment k by visit j , s_i is the random effect of subject i and $\varepsilon_{ij} \sim \text{Normal}(0, \sigma^2)$ represents the residual variance component with $\text{corr}(\varepsilon_{ij}, \varepsilon_{ij'}) = \rho_{jj'}$, $j \neq j'$

As a sensitivity analysis, the MMRM using the above model will also be applied to assessments post-baseline up to termination of study medication or initiation of rescue medication. In addition, the MMRM on all assessments will be repeated including additional effects time on rescue medication and time on study medication. MMRM assumes missing at random; mRSS by time of patient discontinuation from study medication¹²² will be summarized and further methods using multiple imputation that allow for missing data not at random will be investigated. Details of such methods will be described in the SAP.

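### Protocol Section 5.2.1.3 asks for efficacy and vital status to Week 52 from patients who withdraw, then ends eCRF collection 30 (+5) days after the last dose

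*Protocol*

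**What the plan says.** Protocol Section 5.2.1.3 introduces a list of data still to be obtained with the words "A patient may withdraw from further participation in the study and, unless he/she objects to further data collection". The list has three items: vital status at Week 52, the outcome of serious adverse events, and "Efficacy endpoints at Weeks 12, 26, 39, and 52 (depending on timing of discontinuation of study medication". The sentence that follows the list reads: "The information should be collected in the eCRF until the safety follow-up visit 30 (+5) days after the last intake of study drug".

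The same section goes on to say that serious adverse events arising in that period are followed to resolution where possible. It adds that vital status at Week 52 should be sought from public databases for patients who cannot or will not be contacted, where local rules allow. It also says "it is imperative to obtain complete data for all randomized patients, including information on efficacy and safety endpoint events", whether or not the patient stays on drug.

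For patients who stop study drug, Sections 4.1.5, 5.2.1.3 and 7.1.2.10 and footnote v of Table 7-1 offer limited assessments; the three sections place them at Weeks 12, 26, 39 and 52. None of these places states a cut-off. Section 4.1.5 explains their purpose: "The collection of these assessments is important for endpoint analysis which considers all assessments post baseline up to Week 52". Section 8.4.2.1 defines the primary analysis as the "change in mRSS from baseline to all assessments post baseline up to Week 52", fitted by MMRM.

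**The concern.** The cut-off sentence refers back to the list directly above it, and two of the three items in that list are dated Week 52. A patient who leaves early cannot have Week 52 data entered and also have entry closed about a month after the last dose. A site that follows the cut-off closes the record before the later visits.

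What is at stake is the off-drug mRSS and the other efficacy values up to Week 52. The primary analysis is meant to use them, and Section 8.4.2.1 acknowledges that the MMRM assumes missing at random. Values lost because a patient left early belong to the patients for whom that assumption is hardest to defend. Section 5.2.2 rules out replacement, and Section 8.6 allows only for two patients randomized but not treated, so the plan has no reserve for missing Week 52 data.

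**Working it through.** **Inputs.** Cut-off: last dose + 30 to 35 days (Section 5.2.1.3). Visit days and windows (Table 7-1): Week 12, Day 84 ± 2; Week 26, Day 182 ± 2; Week 39, Day 273 ± 14; Week 52, Day 364, −14 to +2. The protocol gives no separate windows for the limited assessments, so the scheduled-visit windows are assumed to apply.

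**Step 1: latest date on which both sentences fail.** A visit lies inside the cut-off only if last dose + 35 ≥ visit day, that is, last dose ≥ visit day − 35. The longer limit, 35 days, favours the plan.

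| Visit | Nominal day | Earliest window day | Last dose needed (nominal − 35) | Last dose needed (earliest − 35) |
|---|---|---|---|---|
| Week 12 | 84 | 82 | 49 | 47 |
| Week 26 | 182 | 180 | 147 | 145 |
| Week 39 | 273 | 259 | 238 | 224 |
| Week 52 | 364 | 350 | 329 | 315 |

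For Week 52 the limits are Day 315 (315/7 = Week 45) and Day 329 (329/7 = Week 47). With 30 days instead of 35 they become 350 − 30 = Day 320 and 364 − 30 = Day 334.

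**Step 2: examples.**
- Last dose Day 70 (Week 10): cut-off by Day 105 (Week 15). Week 12 and the termination visit can be entered; Weeks 26, 39 and 52 cannot.
- Last dose Day 182 (Week 26): cut-off by Day 217 (Week 31). Weeks 39 and 52 are lost.
- Last dose Day 273 (Week 39): cut-off by Day 308 (Week 44). Week 52 is lost, because its window opens on Day 350.

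**Step 3: whom the cut-off covers.** The sentence that introduces the list concerns withdrawal from participation without objection, so the cut-off attaches to that group. The efficacy item, however, is timed by discontinuation of study medication, and the section heading covers both groups. A site could therefore read the cut-off as applying to patients who only stopped drug.

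**Step 4: whether other text removes the cut-off.** The sentence on complete data states the aim without exempting efficacy from the limit. Serious adverse events get an explicit extension past it; efficacy does not. The public-database rule reaches Week 52 for patients who refuse contact or are lost. Read literally, then, vital status is pursued longer for them than for a withdrawer who is willing to be followed. Table 7-1 and Section 7.1.2.9 place survival status only at the safety follow-up visit, which fits the cut-off rather than Week 52.

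**Step 5: sample size.** Section 8.6 is reproducible: with a difference of 4, SD 8, two-sided 5% and 64 per group, the noncentrality is 4 / (8 × √(2/64)) = 2.83 and power is about 80%, as in Table 8-2. That figure takes a Week 52 value for everyone. Moving from it to a power loss needs a share of patients affected, and the documents give none.

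**The case against.** The strongest reply is about scope. Amendment 4 set out to separate leaving the study from stopping drug with data collection continuing. Patients in the second group are invited to visits through Week 52 in several places without a cut-off. Sections 7.6.2 and 7.6.8 expect hemoglobin from those visits to be entered in the eCRF, so entry after the cut-off is plainly foreseen. A reader might infer that everyone who stops drug before about Week 47 loses the Week 52 value. The documents do not support that: the cut-off is written for withdrawers, and a site would have to set aside explicit visit instructions to apply it more widely. This part of the reply stands, apart from the loose wording of the efficacy item.

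A second reply is that the intent is clear from the same section. That is true, and it makes this a wording conflict rather than a flaw in the design. It does not tell a site which of two adjacent sentences to follow.

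Two further inferences are tempting. One is that the CRISS endpoint is left without data for these patients; Section 8.4.2.2 provides model-based estimates of its Week 52 components for patients who stop drug or have components missing. The other is a specific fall in power. That would need an assumed dropout rate, and a complete-case t-test would ignore the earlier visits that the MMRM retains.

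Finally, Amendment 7 was prepared after the main-phase results, so new wording cannot recover main-phase data that were never collected. That also stands.

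**Conclusion.** The conflict is in the current protocol text. For patients who withdraw from participation without objecting, the request for Week 52 data and the 30 (+5) day limit on eCRF collection are compatible only when the last dose is on about Day 315 to Day 329 or later. That excludes stops during roughly the first 45 to 47 of the 52 weeks. If a site applies the limit, later mRSS and other efficacy values that the primary analysis is meant to include are not entered, and the result depends more on missing at random.

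The conclusion rests on reading the cut-off sentence as referring to the list above it and on using the scheduled-visit windows. How many patients are affected is unknown, so the effect on power or bias cannot be given as a number. The SAP supplied covers only the long-term extension and does not settle the point. The main-phase SAP, version 4.0, is not among the documents.

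**What to change.** Restrict the 30 (+5) day sentence to the onset window for adverse events, serious and non-serious, with serious events followed to resolution as already stated. This matches the observation period in Sections 7.5.1.3 and 7.5.1.4.

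Then state two rules:
- mRSS, FVC and DLco, patient-reported outcomes, and the patient's and physician's global assessments are entered in the eCRF through Week 52 for every randomized patient who has not objected to data collection.
- Vital status at Week 52 is recorded for all randomized patients, keeping the existing public-database rule where local regulations allow.

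The cost is one sentence in the protocol and the matching line in the eCRF guide. No visit or procedure is added, because the Week 12 to 52 assessments are already planned.
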